Study Title: Patient Portal Reminder/Recall for Influenza Vaccination in a Health System- RCT 3
Initial IRB Approval: 12/20/2017
RCT 3 IRB Approval: 8/14/2020
Clinical Trials Registration: NCT04533685

Statistical Analysis

Primary Analysis

We hypothesize that patients receiving pre-commitment prompts will have higher vaccination rates than control arm patients; patients sent pre-appointment reminders will have higher vaccination rates than control arm patients; and patients linked to direct scheduling will have higher vaccination rates than control arm patients. Primary outcomes (patient receipt of flu vaccine) are binary; our main explanatory variable will be an indicator for the receipt of any portal-based R/R or prompt.

The analysis will be based on a 2x2x2 nested factorial design, nested in a parallel 2-arm trial RCT, comparing the effectiveness of combining portal R/R with patient direct appointment scheduling vs. portal R/R alone vs. control (no intervention) on influenza vaccination rates. Both treatment groups will be additionally randomized into 4 groups to receive 1) a R/R message only (with or without direct appointment scheduling link), 2) the R/R message and a pre-commitment prompt, 3) the R/R message and pre-appointment reminder or 4) the R/R message, a pre-commitment prompt, and a pre-appointment flu vaccine reminder.

We will employ intent-to-treat analyses using mixed effects log-binomial regression models with practice random effects, an approach recommended for RCTs in which the goal is to estimate the causal effects of interventions on individuals, adjusted for clustering of patients by practice. The primary model terms will be general reminder arm (general reminder v. no general reminder), and interactions between general reminder arm and (1) pre-commitment arm (pre-commitment question v. no pre-commitment question), (2) pre-appointment reminder arm (pre-appointment reminder v. no pre-appointment reminder) and (3) direct scheduling arm (general reminder links v. does not link to direct scheduling).). Models will adjust for the following patient characteristics: age, gender, race/ethnicity, primary language, primary insurer, and prior receipt of influenza vaccines in the last two years. Evaluation of study hypotheses will be performed using model contrasts, and treatment effects will be reported in terms of risk ratios and 95% CIs. In the event of computational issues, we will replace the log-binomial specification with a log-Poisson specification, and use model-robust standard errors for inference on treatment effect risk ratios.

Secondary Analysis

Secondary analyses will include evaluation of process measures (e.g., missed opportunities); evaluation of effect modification by patient characteristics; comparison of receiving precommitment intervention and pre-appointment reminder intervention with not receiving those interventions, however still receiving reminder letters; and evaluation of vaccination receipt including self-reported vaccinations. Process measures will be analyzed similarly to the primary outcome, but using different distributions and link functions as appropriate (e.g., negative binomial distributions for number of missed opportunities). Effect heterogeneity will be evaluated by introducing interaction terms into the primary model specification. All secondary analyses will use a significance level of 0.05. All analyses will be performed using SAS v. 9.4 (SAS Institute Inc., Cary, NC).

Process measures: We assessed the percentage of patients who opened the portal reminder letter, as well as the source of influenza vaccination data (health system within UCLA practices, external source via data transfer, patient/proxy update through normal portal processes, or patient/proxy update in response to portal reminders.

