### Protocol

### **Brief Summary:**

This trial is taking place in Los Angeles, CA among patients from primary care practices within the UCLA Health System.

Despite the Advisory Committee on Immunization Practices (ACIP) recommendation in 2010 that all people above 6 months of age should receive an annual flu vaccine, vaccination rates remain low. The investigators plan to assess the effectiveness of reminder/recall messages (direct appointment scheduling, no direct-appointment scheduling, pre-appointment, and no pre-appointment) encouraging influenza vaccinations sent to patient portal users, as well as the effectiveness of a pre-commitment prompt (pre-commitment prompt, no prompt) asking about a patient's intention to get the influenza vaccination, using a 2 x 2 x 2 nested factorial design.

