## **Inclusion criteria**

Inclusion criteria will involve-- all UCLA primary care patients over 4 months of age who have made at least 1 visit to the practice within the prior 3 years and who have signed up for MyUCLAhealth (UCLA's portal) and have used the portal at least once within 12 months. Currently this includes 298,112 patients; from these patients, index patients per household will be randomly selected.

a. Active patient: We selected >1 visit in 3y based on our prior studies and the literature to focus the intervention on active patients; practices do not have a good mechanism to inactivate patients.

b. Focusing on Portal Users: We can only send portal R/R messages to patients who have signed up for the portal. Since some patients sign up for the portal but never use it we will restrict our inclusion criteria to patients who used the portal within 12m (75% of UCLA patients). This standard has been applied before. We will assess intervention effects for the included population, and also for the entire practice, since the impact of the intervention reflects the extent of portal penetration.

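### The primary hypotheses compare each component with control, so every such contrast includes the reminder effect and can credit a component that adds nothing

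*SAP*

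**What the plan says.** The SAP's Primary Analysis opens with three hypotheses of one form. The first is "We hypothesize that patients receiving pre-commitment prompts will have higher vaccination rates than control arm patients"; the other two put the pre-appointment reminder and the direct-scheduling link in place of the prompt. The same paragraph adds that "our main explanatory variable will be an indicator for the receipt of any portal-based R/R or prompt". The next paragraph names a further three-way comparison: reminder with link, reminder alone, and control.

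The model is an intent-to-treat log-binomial mixed model with a random effect for practice. Its treatment terms are the general reminder arm and the interactions of that arm with prompt, pre-appointment reminder and link. On testing, the SAP says "Evaluation of study hypotheses will be performed using model contrasts". It gives no coding, contrast weights or rule for averaging over the other components.

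Under Secondary Analysis, the prompt and the pre-appointment reminder are compared "with not receiving those interventions, however still receiving reminder letters". The Protocol's Brief Summary states the prompt question as with versus without: "as well as the effectiveness of a pre-commitment prompt (pre-commitment prompt, no prompt". The arm table in the Protocol's Methods and Procedures shows reminder messages in all eight experimental arms.

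**The concern.** A factorial within the treatment arm exists to show what each component adds to the reminder. A component-versus-control contrast cannot show that, because patients given the component also get the reminder and controls are assigned none. If the reminder works and the prompt does nothing, the prompt hypothesis as worded is still true and will often be declared significant. A health system could then adopt a prompt that has no effect. The comparison that would reveal this is labelled secondary for the prompt and the pre-appointment reminder. For the link, it is named under Primary Analysis but is not one of the three hypotheses.

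A second, smaller gap is that the documents do not say which effect is the main one. The any-versus-none average, the reminder-only effect and three component-versus-control effects can all be taken from the same fit, and they differ in value and precision.

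**Working it through.** The plan gives no uptake, effect size, allocation ratio, analysis sample size or power, so there is no figure to reproduce. The only count is in the Protocol's Inclusion criteria: "Currently this includes 298,112 patients", before index patients are drawn from households.

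**Model.** With prompt P, pre-appointment reminder A and link D coded 0/1, and R = 1 in the eight active arms:

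log p = log p0 + R(b0 + b1·P + b2·A + b3·D)

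**What each contrast estimates (log RR, equal active arms)**
- General reminder coefficient: b0, the reminder-only arm versus control
- Any versus none: b0 + (b1+b2+b3)/2
- Prompt versus control, others absent: b0 + b1
- Prompt versus control, averaged: b0 + b1 + (b2+b3)/2
- Prompt versus no prompt among reminder arms: b1

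Only the last is free of b0. The averaged version also takes in half of each other component's log RR.

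**Assumptions.** p0 = 0.45; N = 100,000 or 200,000 index patients; control share c = 1/9 (nine equal arms) or 1/2; two-sided 5%; no adjustment for covariates or practice.

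**Inert components, reminder RR 1.02.** All active arms have p = 0.45 × 1.02 = 0.459. Let Wc = cN × 0.45/0.55 and Wt = (1−c)N × 0.459/0.541. Then:
- Var(others absent) = 1/Wc + 4/Wt
- Var(averaged) = 1/Wc + 2/Wt
- Var(b1) = 4/Wt

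For N = 100,000 and c = 1/9, 1/Wc = 1.100×10⁻⁴ and 1/Wt = 1.326×10⁻⁵. The SEs are 0.01277, 0.01168 and 0.00728. With log 1.02 = 0.0198, z = 0.0198/0.01277 = 1.55, and the chance of exceeding 1.96 is 0.341.

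| N | c | Others absent: SE, P(sig) | Averaged: SE, P(sig) | Prompt v. no prompt: SE, P(sig) |
|---|---|---|---|---|
| 100,000 | 1/9 | 0.01277, 0.341 | 0.01168, 0.396 | 0.00728, 0.050 |
| 100,000 | 1/2 | 0.01090, 0.443 | 0.00846, 0.648 | 0.00971, 0.050 |
| 200,000 | 1/9 | 0.00903, 0.592 | 0.00826, 0.669 | 0.00515, 0.050 |
| 200,000 | 1/2 | 0.00771, 0.729 | 0.00598, 0.911 | 0.00687, 0.050 |

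**Sensitivity**
- Reminder RR 1.04, components inert: 87-100% (others absent) and 92-100% (averaged), against 5%.
- Prompt inert, reminder and the other two components each RR 1.02: the averaged contrast has RR 1.02 × 1.02 = 1.040 and is significant in 92-100%.
- Uptake varied, reminder RR 1.02, same formulas with p0 replaced: 20-46% and 23-67% at 30% uptake; 56-94% and 63-99% at 60%.

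**Any versus none against the reminder coefficient.** With reminder RR 1.00 and each component 1.02, b0 gives RR 1.000 (significant in 5%), while any versus none gives 1.02^1.5 = 1.030 (76-100%). The two agree only if b1+b2+b3 = 0 or the components are centred at ±0.5 within the active arms.

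**The case against.** A reader might infer that the primary effect is undefined. The documents do not support that. Three comparisons with control are put in words and assigned to model contrasts, and all are estimable because the model has full rank. The most that can be said is that the primary effect is not uniquely specified.

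A reader might also infer that the SAP will report the general reminder coefficient as its main result, because "The primary model terms will be general reminder arm (general reminder v. no general reminder") is the first model term and, by assignment, is the same 0/1 column as the any-versus-none indicator. The SAP never says so. The documents agree on the variable; only the coefficient differs, and only under 0/1 coding. On its own, that would be missing detail.

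Two further points stand. The SAP does plan the isolating comparison for the prompt and the pre-appointment reminder, so the correcting result would be produced, though as secondary. It also names link versus reminder alone under Primary Analysis, so that comparison has not been forgotten. Comparing a package with usual care is a legitimate question too.

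The sizes depend on assumed effects. With reminder RR 1.05 and components at 1.02, the reminder coefficient, any versus none and both prompt-versus-control contrasts are all significant in 97-100%. Where contrasts disagree, it is significant against not significant, not a reversed direction. None of this removes the attribution problem: the stronger the reminder, the more often an inert component passes.

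**Conclusion.** The concern holds as a question of attribution. The primary hypotheses, as worded, test reminder plus component against control, while the Protocol asks what the prompt does compared with no prompt. With a reminder RR of 1.02 and inert components, a component would be declared better than control in 34-91% of trials across both versions of the contrast, against 5% for the comparison that isolates it. Those figures rest on assumed uptake, sample size, allocation and effects, because the documents give none. The inclusion of b0 in every component-versus-control contrast follows from the design and rests on no assumption.

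The choice of main effect should also be settled, but it is the lesser issue. The arm-based intent-to-treat model is sound and needs no change. This should be corrected in the SAP; it does not threaten the trial.

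**What to change.** 1. Make the primary test of each component its own interaction term (b1, b2, b3: with versus without, among the reminder arms). This moves the prompt and pre-appointment comparisons from secondary to primary and puts link versus no link on the same footing.
2. Define the main indicator as randomised assignment to any intervention arm versus control. This agrees with intent-to-treat, whereas the present wording speaks of receipt and the Protocol notes that UCLA employees in the control arm are sent a reminder (by a channel it does not state). Write its contrast as b0 + w1·b1 + w2·b2 + w3·b3, where each w is the allocated share of reminder-arm patients assigned that component (1/2 each if the eight arms are equal). Describe the result as an average log RR.
3. If component-versus-control contrasts are kept, call them reminder plus component and state whether the other components are absent or averaged.

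The cost is SAP text only: same model, data and patients. The downside is power, because component claims rest on a smaller effect. For a component RR of 1.02 with reminder RR 1.00 and 45% uptake, log 1.02 = 0.0198 divided by SEs of 0.00721 and 0.00510 (nine equal arms; 100,000 and 200,000 patients) gives 78% and 97% power. SEs of 0.00962 and 0.00680 (half in control) give 54% and 83%. These take 5% per test. The SAP states a significance level only for secondary analyses, so one should be stated for the primary tests as well.
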